## **Study Protocol**

### *Study Design*

This study followed a randomized, double-blinded, crossover design. Participants reported to the clinical site on two separate visits. Participants were instructed to abstain from exercise on testing day and arrive at the lab fasted (no food or caffeine ingestion for 4 hours prior). Testing sessions consisted of two visits per week with a minimum of 24 hours between visits. During the first visit demographics and anthropometrics were assessed. At every testing each subject completed the following protocol: baseline Metabolic Rate and Respiratory Quotient. Immediately after baseline test, participants consumed supplement 1 or 2. Metabolic Rate and Respiratory Quotient Testing was repeated at 60, 120, and 180 minutes after supplementation. All participants underwent an informed consent process in accordance with the Declaration of Helsinki and an approved IRB protocol approved by institutional review board at Nova Southeastern University, IRB number 2024-209.

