### *Metabolic and Respiratory Quotient Testing*

An indirect calorimetry device (Parvo Medics TrueOne 2400) was used to measure RMR and RQ. The device was calibrated according to the manufacturer's instructions. Participants were instructed to lay completely still and relax for 15 minutes. The first 5 minutes was allotted for acclimatization. The Parvo Metabolic Cart measures the volume of oxygen consumed ( $VO_2$ ) and the volume of carbon dioxide produced ( $VCO_2$ ) by the patient on a breath-by-breath basis. The ratio of these gases is used to determine the Respiratory Quotient (RQ), providing information regarding substrate utilization. The parameters that were measured and used for analysis were RMR,  $O_2$  volume ( $VO_2$ ),  $CO_2$  volume ( $VCO_2$ ), the RQ, percentage of utilized fat (Fat%), and percentage of utilized carbohydrates (CHO%).

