## **Statistical Analysis**

All data is expressed as mean SD. Basic descriptive statistics were used for participant demographics and anthropometrics. A paired t-test was used to assess any differences between the 100 and 200 mg doses for REE and RER at baseline. To determine the effects of Gyngerlean™ on energy expenditure, a repeated-measures analysis of variance (ANOVA) was used to determine differences between 100mg and 200mg doses for the 60, 120- and 180-time intervals. A repeated Dunnett's multiple

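### The visible ANOVA sentence for this two-visit crossover names dose and time but not visit; if raw values were compared without a visit term, a shift between visits costs power and, with unequal sequences, biases the dose difference

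*Combined protocol and SAP*

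**What the plan says.** Study Design, in the combined protocol and SAP, states: "This study followed a randomized, double-blinded, crossover design. Participants reported to the clinical site on two separate visits". Each participant therefore received each dose once, and visit and order of dosing are features of the design. Each visit has its own pre-dose measurement ("At every testing each subject completed the following protocol: baseline Metabolic Rate and Respiratory Quotient"), followed by tests at 60, 120 and 180 minutes.

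Statistical Analysis treats baseline separately: "A paired t-test was used to assess any differences between the 100 and 200 mg doses for REE and RER at baseline". For the main comparison it says that "a repeated-measures analysis of variance (ANOVA) was used to determine differences between 100mg and 200mg doses for the 60, 120- and 180-time intervals". That sentence is complete. It names dose and the three post-dose times; it does not name visit or sequence, or say whether the response is the raw value or the change from that visit's baseline. The next sentence, on Dunnett's procedure, is cut off, so neither its comparator nor any later description of the model can be seen.

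Metabolic and Respiratory Quotient Testing lists the analysed parameters as measured quantities and does not mention change. That leans towards raw values without settling it. The visible text gives no sample size, numbers per sequence, alpha, power or randomisation method.

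**The concern.** In a two-period crossover each dose difference within a participant is also a difference between visits. If metabolic rate or respiratory quotient tends to differ between visit 1 and visit 2 for reasons unrelated to dose, that shift is added to the 200 minus 100 mg difference for those who took 100 mg first and subtracted for those who took 200 mg first. A model without visit treats this as random noise. If the two sequences differ in size, the shift does not average out, and part of it is read as a dose effect.

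The comparisons at risk are the dose main effect and the dose difference at each time, on raw values. The visible text does not let a reader tell whether they are protected, either by a visit term or by the use of same-visit changes.

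**Working it through.** The visible text states no sample size or power, so there is no figure of the plan's own to reproduce. The check is algebra, with sizes added under stated assumptions.

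**Inputs.** From the documents: two doses, two visits, a baseline at each visit, three post-dose times. Assumed: n = 12 or 20; splits between sequences of 6/6, 7/5, 8/4, 10/10, 12/8 and 13/7; two-sided alpha of 0.05; a dose effect sized for 80% power with no visit shift (0.889 SD for n = 12, 0.660 SD for n = 20); a shift p, visit 2 minus visit 1, of up to 0.5 SD, constant through the session. SD is that of the raw paired dose difference without a visit effect.

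**Model.** With two doses, the dose main effect and the dose difference at any one time reduce to a paired difference per participant:

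d = δ + s·p + e, with s = +1 if 100 mg came first (n1 participants) and s = −1 if 200 mg came first (n2 participants).

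**Without visit** (paired t-test on d):

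- Bias = p(n1 − n2)/n. This is 0 with equal sequences, 2/12 = 0.17p at 7/5, 4/20 = 0.20p at 12/8, 6/20 = 0.30p at 13/7 and 4/12 = 0.33p at 8/4.
- Expected sample variance of d = SD² + 4·n1·n2·p²/(n(n − 1)), which is about SD² + p² when the sequences are near equal. For 6/6 and p = 0.5 SD: 1 + (4 × 6 × 6 × 0.25)/(12 × 11) = 1 + 36/132 = 1.27 SD².

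**With visit**: the estimate is the average of the two sequence-specific mean differences, with variance pooled within sequence and n − 2 degrees of freedom. Its bias is 0 for any p.

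**Simulated results at p = 0.5 SD:**

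| Split | Bias without visit (SD) | Power without visit, bias opposing the effect | Power with visit | Type I error without visit |
|---|---|---|---|---|
| 6/6 | 0 | 72% | 79% | 3% |
| 10/10 | 0 | 72% | 80% | 3% |
| 7/5 | 0.08 | 63% | 78% | 3.5% |
| 12/8 | 0.10 | 57% | 78% | 4.5% |
| 13/7 | 0.15 | 50% | 76% | 6.5% |
| 8/4 | 0.17 | 54% | 74% | 5.5% |

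(In the two equal-sequence rows there is no bias to oppose the effect.)

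At p = 0.25 SD the consequences are smaller. Equal sequences give 78% power without visit. At 8/4, power without visit is 70% or 85%, depending on whether the bias opposes or favours the effect, against 74% with visit. At 13/7 it is 68% or 86–87%, against 76%. At p = 0.1 SD with equal sequences nothing is lost (about 80%).

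**When the visit term narrows the interval.** Its 95% interval is the shorter one only above a break-even shift of 0.08 SD (10/10), 0.14 (6/6), 0.22 (7/5 and 12/8), 0.33 (13/7) or 0.39 (8/4).

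**Same-visit change.** Subtracting that visit's baseline removes p before the doses are compared. In simulation the bias is 0 and power does not move as p goes from 0 to 1 SD. Power then depends on how much of the paired-difference variance is shared within a visit: about 66%, 80% or 88% when the share is 30%, 50% or 60%. A constant shift also drops out of dose-by-time contrasts (simulated bias 0, type I error about 5%) and of comparisons with baseline within a dose.

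**The case against.** The strongest objection is about evidence. A reader might infer that the analysis left visit out, or that the trial's dose comparison is biased. The documents support neither. The text stops mid-sentence, and visit, sequence or the response scale could follow. Harm also needs several conditions together: raw values, no visit term and a sizeable shift, with unequal sequences as well for bias. None of these is stated. The conditions of testing also work against a large shift: "Participants were instructed to abstain from exercise on testing day and arrive at the lab fasted", and "The device was calibrated according to the manufacturer's instructions". This objection stands, and it is why the point is conditional. It does not remove the point: the ANOVA sentence itself is complete and silent on visit, and standardised conditions reduce a shift without excluding one.

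Second, some of the analysis may be immune. Dunnett's procedure compares several means with one control, and the visible text shows no placebo, so the same-visit baseline is a plausible control. If so, those follow-up tests are unaffected by a constant shift. That stands; the 100 mg versus 200 mg comparisons on raw values remain exposed.

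Third, the paired t-test at baseline is a partial check, because a constant shift would put the same p(n1 − n2)/n into it. It is weak in a small trial and covers two outcomes. With equal sequences the shift averages to zero there, so the test would not reveal it. Nor does it adjust the post-dose comparison.

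Fourth, the gain is small for modest shifts. At p = 0.25 SD the root mean squared error without and with visit is 0.300 and 0.306 (8/4), 0.236 and 0.234 (13/7), 0.230 and 0.229 (12/8), and 0.291 and 0.292 (7/5), in SD units. At p = 0.5 SD and 8/4 the visit term is better, 0.307 against 0.334. This stands too: the case for the term rests on protection against a larger shift.

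**Conclusion.** The point holds in conditional form and is of low priority. If raw post-dose values were compared between doses without visit, a visit shift p adds about p² to the variance of the paired dose difference. With equal sequences the comparison is unbiased and conservative, and power falls from 80% to about 78% at p = 0.25 SD and 72% at p = 0.5 SD. With unequal sequences the dose main effect and per-time dose differences are also biased by p(n1 − n2)/n, for example 0.17 SD at 8/4 with p = 0.5 SD.

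These sizes rest on an assumed n, split and shift, and on a shift that is constant through the session; a visit effect that varied with time after dosing would not cancel from same-visit changes. It would go too far to read the unequal-sequence case as a general excess of false positives: type I error stays at or below 5% at 7/5 and 12/8 for p = 0.25–0.5 SD, and reaches at most 6.5% in the settings tabulated.

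**What to change.** - State whether the analysed response is the raw value or the change from same-visit baseline.
- Report the number of participants in each sequence.
- If raw values were analysed and visit is not already in the model, add visit as a fixed effect to the 100 mg versus 200 mg comparison. A sequence term is optional; nothing in the calculations above supports requiring it.
- If visit was already fitted, one sentence saying so is enough. If same-visit changes were analysed, no refit is needed to remove a constant shift.

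Cost: wording, plus a refit in the one case named, using visit data that should already be recorded. The visit term takes one degree of freedom. If there is in fact no visit effect, it lowers power by under 1 point with equal sequences, about 2 points at 7/5 or 12/8, about 4 at 13/7 and about 6 at 8/4.
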